10.2 ARCHIVING

It is the responsibility of the Investigator to ensure all essential study documentation and source records (e.g. signed Informed Consent Forms, Investigator Site File, patients' hospital notes, copies of CRFs etc) at their site are securely retained for at least 5 years after the end of the study. Do not destroy any documents without prior approval from the CRCTU Document Storage Manager.

11. QUALITY MANAGEMENT

ArChIMEDEs-Op study will be coordinated by the Cancer Research UK Clinical Trials Unit at the University of Birmingham according to the current guidelines for Good Clinical Practice (GCP).

11.1 ON SITE MONITORING

Monitoring will be carried out as required following a risk assessment and as documented in the ArChIMEDEs-Op Quality Management Plan according to CRCTU policy. On-site monitoring visits may be triggered for example by poor CRF return, poor data quality, low SAE reporting rates, excessive number of patient withdrawals or deviations. If a monitoring visit is required the ArChIMEDEs-Op Study Office will contact the site to arrange a date for the proposed visit and will provide the site with written confirmation. Investigators will allow the ArChIMEDEs-Op study staff access to source documents as requested.

11.2 CENTRAL MONITORING

Where a patient has given explicit consent sites are requested to send in copies of signed Informed Consent Forms for in-house review.

Study staff will be in regular contact with the site research team to check on progress and address any queries that they may have. Study staff will check incoming CRFs for compliance with the protocol, data consistency, missing data and timing. Sites will be sent Data Clarification Forms requesting missing data or clarification of inconsistencies or discrepancies.

Sites may be suspended from further recruitment in the event of serious and persistent non-compliance with the protocol and/or GCP, and/or poor recruitment. Any major problems identified during monitoring may be reported to Trial Management Group. This includes reporting serious breaches of GCP and/or the study protocol to the REC.

11.3 AUDIT AND INSPECTION

The Investigator will permit study-related monitoring, audits, ethical review, and regulatory inspection(s) at their site, providing direct access to source data/documents.

11.4 NOTIFICATION TO SPONSOR

The Sponsor of the Study is responsible for notifying the REC in writing of any serious breach of the protocol relating to the study, within 7 days of becoming aware of that breach. A "serious breach" is defined as a breach which is likely to effect to a significant degree:

- The safety or physical or mental integrity of the subjects of the study; or
- The scientific value of the study

The investigator is therefore requested to notify the ArChIMEDEs-Op Study Office of a suspected study-related serious breach of GCP and/or the study protocol. Where the ArChIMEDEs-Op Study Office is investigating whether or not a serious breach has occurred, the site is also requested to cooperate with the ArChIMEDEs-Op Study Office in providing sufficient information to report the breach to the REC and in undertaking any corrective and/or preventive action.

12. STATISTICAL CONSIDERATION

12.1 POWER CALCULATIONS

The trial design is a single stage feasibility study of 15 patients.

12.2 ANALYSIS OF OUTCOME MEASURES

The primary outcome measure will be reported as the percentage of recruited patients with treatment 'success' together with an associated 95% confidence interval.

Categorical data will be reported descriptively as percentages with 95% confidence intervals. Time to event data will be analysed using the Kaplan-Meier method of estimation and survival estimates presented with 95% confidence intervals.

12.3 PLANNED SUB-GROUP ANALYSES

There are no planned sub-group analyses.

12.4 PLANNED FINAL ANALYSES

The final analysis of the primary outcome measure will take place as soon as all registered patients had completed treatment and been followed up for 3 months. Other secondary outcomes that could be reported at this time include duration of Grade 3 mucositis, incidence of Grade 4 toxicity and response rate. Longer follow-up would be needed for other secondary outcome measures with final analysis when patients have been followed up for a minimum of 5 years.

12.5 EARLY STOPPING RULE

The occurrence of Grade 3 mucositis in 2 patients at 90 days (assessment week 13). ≥ Grade 3 late RT induced complication in more than 2 patients at one year.

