- 2 year overall survival defined in whole days as the time from entry into the study until death from any cause. Patients will be censored at the date last seen alive. All patients will be followed up for at least 5-years
- Incidence of feeding tube dependency at one year defined by the patient requiring supplementation of nutrition by a feeding tube

PATIENT POPULATION

Patients with HPV and P16 negative locally advanced squamous carcinoma of the oropharynx or patients with P16 positive tumours if stage N2b-3 and greater than 10 pack year history of smoking

SAMPLE SIZE

15 patients

INCLUSION CRITERIA

- 1. Histologically proven, P16 negative SCCOP deemed suitable for radical primary chemoradiotherapy with curative intent requiring bilateral neck irradiation or patients with P16 positive tumours if stage N2b-3 and greater than 10 pack year history of smoking. Neoadjuvant chemotherapy and pre or post chemoradiation neck dissections are permitted
- 2. Only patients requiring bilateral radiotherapy
- 3. Age ≥18 and <75 years
- 4. World Health Organisation (WHO) performance status 0 or 1
- 5. Adequate bone marrow: absolute neutrophil count > 1,800 cells/mm³, platelets > 100,000 cells/mm³, haemoglobin > 8.0 g/dl
- 6. Creatinine clearance > 50 ml/minute
- 7. Informed consent

Clinical and pathological staging is performed according to the International Union Against Cancer, Classification of Malignant Tumours Staging Manual (UICC TNM) -6th edition (Sobin, 2002).

EXCLUSION CRITERIA

- 1. Prior invasive malignancy (except basal cell carcinoma and cervical intraepithelial neoplasia) within last 3 years
- 2. Prior radiotherapy to the head and neck region
- 3. Pregnancy and/or lactation
- 4. Reproductive capability and dis-agreement to use contraceptive
- 5. Contraindications to cisplatin and carboplatin chemotherapy including active vascular disease (e.g. myocardial within last 6 months, angina and symptomatic peripheral vascular disease)
- 6. Non curative intent
- 7. Non squamous cell carcinoma histology
- 8. Nasophaynx, larynx, hypopharynx, salivary gland or sino-nasal primary site
- 9. Other physical or psychiatric disorder that may interfere with subject compliance, adequate informed consent, follow up or determine the causality of adverse events
- 10. Suitable for unilateral radiotherapy

TRIAL DURATION

24 months

STUDY OFFICE CONTACT DETAILS

Enquires:

ArChIMEDEs-Op Study Office

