7.2 INTENSITY MODULATED RADIOTHERAPY DELIVERY

7.2.1 Treatment Schedule

Treatment should begin within 3-4 weeks of consenting to the study and within 8 weeks from diagnosis unless the patient is having neo-adjuvant chemotherapy in which radiotherapy will commence following induction chemotherapy. The planned duration of treatment is 5 weeks. Radiotherapy should commence on a Monday. If radiotherapy cannot be started on a Monday, compensation in the form of a Saturday treatment or double treatments within one day is required.

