8.4 FOLLOW-UP ASSESSMENTS

All patients, provided that they have not withdrawn consent to follow-up, should have long-term follow-up of at least 5 years, irrespective of whether they discontinued study treatment prematurely. The anticipated frequency is:

Early Post Radiotherapy Follow-up:

 Weekly follow-up and documentation of acute toxicity for a minimum of 6 weeks post radiotherapy or until resolution of Grade 3 mucositis

Late Follow-up and Response Assessment:

- Local control documentation at 3 months determined by clinical evaluation (including nasoendoscopy) and MRI scan of head and neck. Directed biopsy should be performed in patients with suspicion of local residual disease and a neck dissection is required for patients with persistent neck disease (clinical or radiological suspicion)
- Thereafter, follow-up according to established local protocols (for example, monthly for the 1st year and every 8 weeks for the 2nd year)
- Documentation of local control and disease free survival is required at 12 and 24 months
- Late toxicity assessment will be recorded at 3, 6, 12, 18, 24 36, 48 and 60 months using NCI CTCAE version 4 and RTOG scoring systems

SCHEDULE OF EVENTS FLOWCHART

Assessment	Screening	Pre-study Entry	Pre- radiotherapy	During Radiotherapy (week)					Early Post Treatment (week)							Long term follow up (month)								
		T		1	2	3	4	5	6	7	8	9	10	11	12	3	6	12	18	24	36	48	60	
Obtain consent	x	x																						
Confirm Eligibility (including CXR;FBC;CrCl)	x	×																						
Histology report including p16 and HPV	*	x																						
Staging CT/MRI H&N		x																						
Dental assessment			х																					
Nutrition assessment			x	X	х	x	X	х																
Plan evaluation			х																					
Baseline toxicity			x																					
Acute toxicity					х	x	x	х	х	х	x	х	х	х	х									
Chemotherapy and Radiotherapy compliance									х															
Late toxicity																х	X	Х	Х	Х	х	х	X	
Disease response																х	x	X	х	X	х	х	X	

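### The late-toxicity stopping limb does not say whether it counts status at the 12-month visit or any event up to one year; on the first reading it gives little protection during accrual

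*Protocol*

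**What the plan says.** Section 12.5 of the Protocol lists two conditions. The early one is "The occurrence of Grade 3 mucositis in 2 patients at 90 days (assessment week 13". The late one is "≥ Grade 3 late RT induced complication in more than 2 patients at one year". The section gives no denominator. It does not say what is stopped, who decides, or whether entry pauses while patients mature.

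Section 8.4 schedules late-toxicity assessment at 3, 6 and 12 months and then out to 60 months. The form table in section 10.1 counts follow-up visits from the end of treatment. Section 7.2.1 says "Treatment should begin within 3-4 weeks of consenting to the study", later if induction chemotherapy is given, and treatment lasts 32 days. Section 12.1 says "The trial design is a single stage feasibility study of 15 patients". No recruitment period or accrual rate appears anywhere.

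Under "TRIAL DURATION" the synopsis gives 24 months. The same synopsis says "All patients will be followed up for at least 5-years", section 8.4 says patients "should have long-term follow-up of at least 5 years, irrespective of whether they discontinued study treatment prematurely", and section 12.4 ties the remaining secondary outcomes to a report "with final analysis when patients have been followed up for a minimum of 5 years". Section 13 ends the study at the last data capture.

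**The concern.** A stopping rule is useful only if it can act while patients are still being entered. A condition judged one year after treatment, in a trial of 15, may mature only when most patients are already in. Section 1.1 acknowledges concern over larger doses per fraction and says that any benefit must be balanced against toxicity. The late limb is the only numerical stop for late damage.

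The wording carries a second risk. If the limb describes status at the 12-month visit, a patient with a Grade 3 complication at 3 or 6 months who has since died or improved is not counted, although the protocol collects that information. Two people applying the rule in good faith could reach different counts.

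**Working it through.** The plan gives no operating characteristics for this rule, so there is no stated figure to reproduce. What follows is a calendar calculation.

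**Inputs from the Protocol.** 15 patients (12.1). More than 2 means at least 3 (12.5). Up to 4 weeks from consent to treatment (7.2.1), rounded to 1 month. Treatment of 32 days. Late visits at 3, 6 and 12 months (8.4), counted from the end of treatment (10.1).

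**Assumptions.** Even accrual over A months with the first entry at month 0. Spacing is A/15 or A/14, the latter putting the 15th entry exactly at month A. Patients are independent with a common true late rate p. Neither A nor p is in the Protocol, so a range is shown.

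**Step 1: lag from entry to the one-year visit.** 1 + 32/30.4 + 12 = 14.05 months.

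**Step 2: earliest possible trigger.** The limb needs three patients. If the first three are all affected, it fires at (third entry) + 14.05, and the third entry is at twice the spacing.

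| A (months) | Third entry | Earliest trigger | Entered by then |
|---|---|---|---|
| 12 | 1.6-1.7 | 15.7-15.8 | 15 |
| 18 | 2.4-2.6 | 16.5-16.6 | 13-14 |
| 24 | 3.2-3.4 | 17.3-17.5 | 11 |
| 36 | 4.8-5.1 | 18.9-19.2 | 8 |

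**Step 3: chance of acting before the 15th entry, 12-month-visit reading.** Let m be the number of patients who have reached one year when the 15th enters. The chance is P(X ≥ 3), with X binomial(m, p).

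| A (months) | m | p = 30% | p = 40% |
|---|---|---|---|
| 12 | 0 | 0% | 0% |
| 18 | 3-4 | 3-8% | 6-18% |
| 24 | 6 | 26% | 46% |
| 36 | 9 | 54% | 77% |

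For example, with A = 18 and m = 3 the chance is 0.3³ = 0.027.

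**Step 4: what changes if events count when first seen.** In a simulation (8,000 trials per setting, 0.8 month from entry to treatment start, spacing A/15), each affected patient's event is assumed equally likely to appear at 3, 6 or 12 months. At p = 30% the chance of acting before the 15th patient starts radiotherapy is:

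| A (months) | 12-month visit only | Counted when seen |
|---|---|---|
| 12 | 0% | 18% |
| 18 | 9% | 44% |
| 24 | 26% | 56% |

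With A = 24 and p from 20% to 40%, the mean number not yet started when the limb fires (taken as zero if it never does) rises from 0.2-1.0 to 1.0-3.5 patients. The gain depends on how early events appear; the equal split is an assumption.

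**Step 5: chance of ever reaching 3 of 15.** Binomial(15, p): 3.6% at p = 5%, 18% at 10%, 60% at 20%, 87% at 30%.

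**Step 6: duration.** One patient needs about 1 + 1.05 + 60 = 62 months. With 24 months of accrual the total is about 86 months, against 24 in the synopsis.

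**The case against.** The strongest reply is that the calendar rests on an accrual period the Protocol never gives. A reader might infer from the 24-month duration that recruitment must be nearly complete by months 16 to 18. The documents do not support this, because that figure cannot be the whole trial length and so cannot be relied on to bound recruitment. If it is the recruitment period, 11 of 15 are entered at the earliest trigger, not all. With 36 months the number is 8. This objection stands, and the point is therefore conditional on accrual.

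The second reply is that the phrase can mean by one year. Late toxicity is recorded from 3 months, and on that reading the limb already works as the fix proposes. This also stands in part. The parallel mucositis limb ties its time point to a named assessment week, which favours the visit reading but does not settle it.

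Third, other safeguards exist. The mucositis limb acts earlier, Grade 4 or worse late effects go on SAE forms for 5 years (9.1.1), the TMG reviews all toxicity reports (14.3), and the ethics committee is told at once of a significant safety issue (9.2.3.2). These are real, but none supplies a count for Grade 3 late complications. Nor can late damage be called the main risk of this schedule: section 1.1 predicts slightly higher mucosal and lower late toxicity than the cited dose-escalation arm.

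Finally, a one-year criterion aimed at persistent damage is a defensible choice, if that is what is intended and stated.

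**Conclusion.** The concern holds as a defect of wording with a conditional consequence. Section 12.5 leaves two readings open, and they behave very differently: with 18-month accrual and a 30% rate, about 9% against 44% for acting before the last patient starts radiotherapy, under the timing assumed above. On the 12-month-visit reading with accrual of 24 months or less, the late limb gives little protection during accrual and ignores earlier events that have resolved or ended in death.

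A reader might go further and conclude that the rule can protect nobody. That does not follow: it could act before the 15th entry in 46% of trials at a 40% rate with 24-month accrual, and in 54% at a 30% rate with 36-month accrual.

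The duration conflict needs no assumption, since 24 months cannot contain 5 years of follow-up. It is a separate and minor matter: the operational sections agree with each other, and the synopsis line would not change conduct.

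**What to change.** Keep the protocol's own limit of more than 2 patients. State in section 12.5 that each patient's first Grade 3 or worse late radiotherapy complication counts when it is recorded at any scheduled late-toxicity visit up to and including 12 months (3, 6, 12), and that the TMG checks the running count as forms arrive. If persistence at 12 months is what is intended, say so and accept the timing above.

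The cost is amendment wording, since the visits and forms already exist. There is a statistical cost too. Transient early events would count, so the cumulative rate that matters is higher than the rate at 12 months; the chance of ever reaching 3 of 15 is 3.6%, 18% and 60% at cumulative rates of 5%, 10% and 20%. Mucosal ulceration persisting at 3 months could count under both limbs, because confluent ulceration is Grade 3 mucositis in Appendix 1 and ulceration is Grade 4 late mucous-membrane toxicity in Appendix 2. The amendment should say how such a case is handled.

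Separately, reconcile the synopsis duration with sections 8.4, 12.4 and 13, for example by labelling the 24 months as the recruitment period if that is what is meant.

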13. END OF STUDY DEFINITION

The end of study will be the date of the last data capture. The ArChIMEDEs-Op Study Office will notify the REC that the study has ended and a summary of the clinical study report will be provided within 12 months of the end of study.

14. STUDY ORGANISATIONAL STRUCTURE

14.1 SPONSOR

The ArChIMEDEs-Op study will be sponsored by University Hospitals Birmingham NHS Foundation Trust.

14.2 CO-ORDINATING CENTRE

The study is being conducted under the auspices of the CRCTU according to their local procedures.

14.3 TRIAL MANAGEMENT GROUP

The Investigator, Co-investigators, Trial Statistician, Senior Trial Manager and Trial Coordinator will form the Trial Management Group (TMG). The TMG will be responsible for the day-to-day conduct of the study. They will be responsible to study set-up, and on-going management of the study, the interpretation of the results and preparation and presentation of relevant publications. The TMG will be responsible for the review of:

- · All reports of toxicity and line listings of SAEs
- Partient's withdrawals
- Accrual rates
- Completeness of data
- Efficacy data

14.4 FINANCE

This is a clinician-initiated and clinician-led study funded by Queen Elizabeth Hospital Birmingham Charities. No individual per patient payment will be made to the NHS Trust, Investigators or patients.

15. ETHICAL CONSIDERATION

The study will be conducted in accordance with the Research Governance Framework for Health and Social Care, the applicable UK Statutory Instruments, (which include the Data Protection Act 1998 and Human Tissue Act 2008) and the International Conference on Harmonisation Guidelines for Good Clinical Practice (ICH GCP). The study will be submitted to and approved by the REC prior to circulation.

Before any patients are enrolled into the study, the Investigator is required to obtain local Research and Development (R&D) approval. The site will not be permitted to enrol patients until written confirmation of R&D approval is received by the ArChIMEDEs-Op Study Office.

It is the responsibility of the Investigator to ensure that all subsequent amendments gain the necessary local approval. This does not affect the individual clinicians' responsibility to take immediate action if thought necessary to protect the health and interest of individual patients.

16. CONFIDENTIALITY AND DATA PROTECTION

Personal data recorded on all documents will be regarded as strictly confidential and will be handled and stored in accordance with the Data Protection Act 1998. With the patient's consent, their specific patient identifiers e.g. patient initials, date of birth, hospital number will be collected at study entry. Patients will be identified using only their unique RNO, initials, hospital number and date of birth on the CRFs and correspondence between the ArChIMEDEs-Op Study Office and the site. However patients are asked to give permission for the ArChIMEDEs-Op Study Office to be sent copies of their signed Informed Consent Forms which will not be anonymised. This will be used to perform in-house monitoring of the consent process. The Investigator must maintain documents not for submission to the ArChIMEDEs-Op Study Office (e.g. Patient Identification Logs) in strict confidence. In the case of specific issues and/or queries from the regulatory authorities, it will be necessary to have access to the complete study records, provided that patient confidentiality is protected.

The ArChIMEDEs-Op Study Office will maintain the confidentiality of all patient's data and will not disclose information by which patients may be identified to any third party other than those directly involved in the treatment of the patient and organisations for which the patient has given explicit consent for data and tissue transfer (e.g. Laboratory staff at Newcastle-upon-Tyne Hospitals Foundation Trust). Pathology Reports and screening results sent by Pathology Laboratory, Newcastle-upon-Tyne Hospitals Foundation Trust to CRCTU will be identified using only patient's RNO, patient initials, hospital number and date of birth. Representatives of the ArChIMEDEs-Op study team may be required to have access to patient's notes for quality assurance purposes but patients should be reassured that their confidentiality will be respected at all times.

17. INSURANCE AND INDEMNITY

The ArChIMEDEs-Op study will be run by CRCTU, University of Birmingham. The University Hospitals Birmingham NHS Foundation Trust will act as the study sponsor. University of Birmingham employees are indemnified by the University insurers for negligent harm caused by the design or co-ordination of the clinical trials they undertake while in the University's employment.

NHS Trust and non-Trust hospitals have a duty to care for patients treated, whether or not the patient is taking part in a clinical trial. Compensation is therefore available via NHS indemnity in the event of clinical negligence having been proven.

The University of Birmingham cannot offer indemnity for non-negligent harm. There are no specific arrangements for compensation made in respect of any SAEs occurring through participation in the study, whether from side effects listed or others yet unforeseen.

18. PUBLICATION POLICY

Results of this study will be submitted for publication in a peer reviewed journal. The manuscript will be prepared by the TMG and authorship will be determined by mutual agreement.

Any secondary publications and presentations prepared by Investigators must be reviewed by the TMG. Manuscripts must be submitted to the TMG in a timely fashion and in advance of being submitted for publication, to allow time for review and resolution of any outstanding issues. Authors must acknowledge that the study was performed with the support of University Hospitals Birmingham NHS Foundation Trust and CRCTU.

